2.5 Randomization and Blinding

This is an open-label study and does not involve randomization or blinding.

3 General

Categorical data will be summarized with counts and percentages. Percentages will be calculated based on the number of non-missing values and will be reported to one decimal place.

Continuous data will be summarized with descriptive statistics including the number of non-missing values, mean, standard deviation, standard error, median, minimum, and maximum. Minimum and maximum will be reported to the same precision as the raw values, mean and median will be reported to one additional decimal place, and standard deviation and standard error will be reported to two additional decimal places.

All data will be listed. When listings are provided instead of summaries or require additional description, they are described in this document.

3.1 Adjustments for Covariates

No statistical modeling will be performed so adjustment for covariates is not planned.

3.2 Handling of Dropouts or Missing Data

As there is no effective treatment for subjects with FOP, it is assumed they will be highly motivated to adhere to the protocol and treatment visits. Thus, it is expected that there will be minimal missing data, and most subjects will complete the study. The efficacy analysis will be performed using observed data only. Missing efficacy data will not be imputed.

3.3 Interim Analyses

No interim analysis is planned.

3.4 Multicenter Studies

A review of by-center effects will be performed in the context of data listing review. However, the sample size precludes formal assessment of by-center effects.

3.5 Multiple Comparison/Multiplicity

As this is an extension of an initial proof-of-concept study, no adjustment for multiple testing is planned.

3.6 Examination of Subgroups

The sample size in this study is not sufficient to allow rigorous assessment of outcomes by subgroups, and the study is not powered for subgroup assessment. However, exploratory assessments of the outcomes may be performed with a limited number of extrinsic or intrinsic factors, including age of the subject, location of the flare-up, amount of new HO, number of flare-up treatments, or other variables as appropriate.

3.7 Part B Study Day, Non-Flare-up Day, and Flare-up Day

For all subjects, Study Day will be determined from the date of informed consent (Part B Study Day 1); Part B Study Day -1 will be the day immediately prior to Part B Study Day 1.

For subjects receiving non-flare-up based treatment, Non-Flare-up Day will be determined from the date of first dose of non-flare-up treatment (Part B Non-Flare-up Day 1).

For subjects receiving flare-up treatment, Flare-up Day will be determined from the date of first dose of flare-up treatment (Flare-up Day 1).

4 Analysis Populations

There will be seven Part B populations defined for the analysis.

4.1 Enrolled Population

The Enrolled Population will include all subjects enrolled in Part B. The Enrolled Population will be the primary population for demographic and baseline summaries and for analysis of adverse events.

4.2 Treated Population

The Treated Population will include all subjects who took at least one dose of palovarotene in Part B (either flare-up treatment or non-flare-up treatment). The analysis will be stratified as follows: PVO 20/10 mg only (including weight-adjusted doses), PVO 20/10 mg (including weight-adjusted doses) with prior non-flare-up treatment, and non-flare-up treatment only.

4.3 Flare-up Population

The Flare-up Population will include all subjects in the Treated Population who took at least one dose of flare-up based treatment in Part B. The analysis will be stratified based on subjects who took PVO 20/10 mg only (including weight-adjusted doses) and subjects took PVO 20/10 mg (including weight-adjusted doses) with prior non-flare-up treatment.

4.4 Flare-up Per Protocol Population

The Flare-up Per Protocol (PP) Population will include all subjects in the Flare-up Population with no major protocol deviations that may impact the efficacy assessment and who were at least 80% compliant with flare-up dosing. Exclusions from the Flare-up PP Population will be identified prior to database lock. The analysis will be stratified as before for the Flare-up Population.

4.5 Pharmacokinetic Population

The Pharmacokinetic (PK) Population will include all subjects in the Flare-up Population who have sufficient blood samples collected for valid estimation of PK parameters. The analysis will be stratified as before for the Flare-up Population.

4.6 WBCT Population

The WBCT Population will include subjects in the Flare-up Population who had prior non-flare-up treatment and have Baseline and Month 12 WBCT scans.

4.7 WBCT Per-Protocol Population

The WBCT Per-Protocol Population will include all subjects in the WBCT Population with no major protocol deviations that may impact the efficacy assessment and who were at least 80% compliant with non-flare-up dosing. Exclusions from the WBCT PP Population will be identified prior to database lock.

4.8 Non-Flare-up Treated Population

The Non-Flare-up Treated Population will include all subjects in the Treated Population who took at least one dose of non-flare-up based treatment in Part B. The Non-Flare-up Treated Population will be used to assess safety data for non-flare-up based treatment assessments.

5 Subject Data

In general, subject data will be summarized for the Enrolled Population by cohort and in total.

5.1 Subject Disposition and Analysis Populations

The following will be summarized with counts and percentages using the number of subjects in the Enrolled Population as the denominator:

- Subjects who were enrolled (Enrolled Population).
- Subjects in the Enrolled Population who took at least one dose of palovarotene (Treated Population).
- Subjects in the Treated Population who took at least one dose of flare-up based palovarotene (Flare-up Population).
- Subjects in the Flare-up Population who did not have major protocol deviations that may impact the efficacy assessment and were at least 80% compliant with flare-up dosing (Flare-up PP Population).
- Subjects in the Flare-up Population who had sufficient blood samples collected for valid estimation of PK parameters (PK Population).
- Subjects in the Flare-up Population who took at least one dose of non-flare-up based palovarotene and also have Baseline and Month 12 WBCT scans (WBCT Population).
- Subjects in the WBCT Population who did not have major protocol deviations that may impact the efficacy assessment and were at least 80% compliant with non-flare-up dosing (WBCT PP Population).
- Subjects who discontinued from Part B early along with reasons for discontinuation.
- Subjects who completed Part B.
- Duration of participation in Part B. This will be calculated from the date of informed consent to the date of completion of Part B/discontinuation.

- Months of participation calculated as days of participation / 30.5. Months of participation will also be summarized with counts and percentages of subjects in the Enrolled Population according to the following categories:
 - ≤ 6 months
 - $>6 - 12$ months
 - $>12 - 18$ months
 - $>18 - 24$ months

Summaries will be presented for the following groups: subjects receiving non-flare-up based treatment only, subjects receiving flare-up based treatment only, and subjects receiving both non-flare-up based and flare-up based treatment.

5.2 Eligibility Criteria

Eligibility criteria (inclusion/exclusion) will be listed with any specific criteria that were not met shown in the by-subject listing for the Enrolled Population.

5.3 Protocol Deviations

Major protocol deviations will be identified prior to locking the database for Part B and may include, but are not limited to departures from the inclusion/exclusion criteria, non-compliance with investigational product, use of restricted concomitant medications, and non-compliance with study procedures. Major protocol deviations will be summarized for the Enrolled Population.

5.4 Demographic and Other Baseline Characteristics

Demographic and other baseline characteristics such as age, sex, race, ethnicity, height, and weight will be summarized for all analysis populations.

5.5 Medical History

Medical history will be coded using the Medical Dictionary for Regulatory Activities (MedDRA Version 17.0). The incidence of medical history conditions will be summarized by MedDRA body system and preferred term for the Enrolled Population.

5.6 Treated Flare-ups Starting During Part B

The number of treated flare-ups will be summarized with counts and percentages of subjects in the Flare-up Population and Flare-up PP Population. Similar summaries will be provided for the number of flare-ups with dosing extended beyond 12 weeks, the number of flare-ups for which an interruption of study drug occurred during flare-up dosing, and the number of flare-ups for which study drug was discontinued during flare-up dosing.

Treated flare-up data as reported by the subject and the Investigator including symptoms, probable causes, and location(s) will be summarized for the Flare-up and Flare-up PP Populations.

The number of days after flare-up onset to the date of first dose of study drug for the flare-up will be summarized for the Flare-up Population with descriptive statistics.

Data for untreated flare-ups will be listed.

5.7 Concomitant Medications

Concomitant medications will be coded using the WHO Drug Dictionary (March 2014). Glucocorticoids taken for a flare-up are defined as courses of glucocorticoids that start within 9 days after the start of the flare-up and are specified as taken for the current flare-up on the electronic case report form (eCRF). Courses of glucocorticoids are defined as days of continuous treatment allowing for up to a 2-day interruption.

The use of the following concomitant medications will be summarized by anatomic therapeutic class (ATC) term and preferred term for the Enrolled Population:

- Prior medications that were on-going at Study Day 1 excluding glucocorticoids. (Medications with start date before Study Day 1 and end date on or after Study Day 1.)
- New-onset medications outside flare-up based treatment periods excluding glucocorticoids. (Medications with start date on or after Study Day 1 and not during Flare-up Day 1 through Flare-up Day 84/EOT.)
- Glucocorticoids outside flare-up based treatment periods that were on-going at Study Day 1. (Courses of glucocorticoids with start date before Study Day 1 and end date on or after Study Day 1.)
- New-onset Glucocorticoids outside flare-up based treatment periods. (Courses of glucocorticoids with start date on or after Study Day 1, not during Flare-up Day 1 through Flare-up Day 84/EOT, and are specified as not being taken for a flare-up.)

The use of the following concomitant medications will be summarized by ATC term and preferred term for the Flare-up Population:

- Prior medications that were on-going at Flare-up Day 1 excluding glucocorticoids. (Medications with start date before Flare-up Day 1 and end date on or after Flare-up Day 1.)
- New-onset medications during flare-up based treatment periods excluding glucocorticoids. (Medications with start date during Flare-up Day 1 through Flare-up Day 84/EOT.)
- Glucocorticoids taken for treated flare-ups defined as courses of glucocorticoids that start within 9 days after the start of the flare-up and are specified as taken for the current flare-up on the eCRF.
- New-onset glucocorticoids during flare-up based treatment periods defined as courses of glucocorticoids that start more than 9 days after the start of the flare-up or are specified as not being taken for the current flare-up on the eCRF.

For the purposes of analysis, incomplete medication start and stop dates will be imputed. If a medication start date is incomplete, January will be imputed for missing month and/or the first day of the month will be imputed for missing day. If a medication stop date is incomplete,

December will be imputed for missing month and the last day of the month will be imputed for missing day. If the imputed medication stop date is after the date of study completion, the date of study completion will be used instead.

A listing of courses of glucocorticoids will include additional derived data such as start and stop dates, based on the first dose date of flare-up treatment, with associated Flare-up Day, start day of the glucocorticoid relative to the start of the flare-up onset date, duration of use, and total amount taken.

5.8 Exposure

Exposure to flare-up based treatment for each treated flare-up will be calculated from the date of first dose for the flare-up to the date of last dose for the flare-up. Days of exposure to flare-up based treatment will be summarized for the Flare-up Population with descriptive statistics. Similarly, exposure to high flare-up treatment (the 20-mg dose), low flare-up treatment (the 10-mg dose), and non-flare-up treatment (5 mg) will be summarized. Separate summaries will include and exclude weight-adjusted doses.

Weeks of exposure to flare-up based treatment will be summarized with counts and percentages of flare-ups in the Flare-up Population according to the following categories:

- ≤ 2 weeks
- $>2 - 4$ weeks
- $>4 - 6$ weeks
- $>6 - 8$ weeks
- $>8 - 10$ weeks
- $>10 - 12$ weeks
- >12 weeks

Months of exposure to non-flare-up based treatment will be summarized with counts and percentages in the Non-Flare-up Treated Population according to the following categories:

- $>0 - 3$ months
- $>3 - 6$ months
- $>6 - 9$ months
- $>9 - 12$ months
- >12 months

Total exposure to study drug for each subject will be calculated as the number of days exposed to study drug. For subjects who received only flare-up based treatment, total exposure is the sum of the exposure for each flare-up. Note that this calculation excludes days between flare-ups. For subjects who received non-flare-up based treatment, total exposure is calculated from the date of first dose of study drug to the date of last dose of study drug, adjusting for any days of study drug interruption. Days of exposure will be summarized with counts and percentages of subjects in the Treated Population.

Dose reductions (no dose reductions, any dose reductions) will be summarized with counts and percentages of flare-ups and subjects in the Treated Population. Similarly, dose reduction categories (ie, 20 to 15 mg, 20 to 10 mg, etc.) will be summarized with counts and percentages.

The number of subjects who experienced an interruption of study drug during non-flare-up dosing and the number of subjects who discontinued study drug during non-flare-up dosing will be summarized with counts and percentages.

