3.2.3 Duration of Flare-up Treatment

For subjects receiving flare-up treatment, duration of flare-up treatment (days) is defined as total flare-up cycle dosing periods (days) across all flare-up cycles.

For a flare-up cycle, the flare-up cycle dosing period (days) is defined as days that subjects received flare-up based treatment and is calculated as (last dose date of the flare-up cycle – first date of the flare-up cycle – days where flare-up meds were not taken/interrupted during the flare-up cycle + 1).

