3.2.4 Duration of Non-Flare-up Treatment

Based on study design, subjects are assumed to be on non-flare-up based treatment from the date they received first non-flare-up treatment unless they receive flare-up based treatment. Thus, duration of non-flare-up treatment (days) will be calculated as (last non-flare-up treatment date - first non-flare-up treatment

date – duration of flare-up treatment (days) - days where non-flare-up meds were not taken/interrupted + 1). Duration of flare-up treatment (days) is defined in 3.2.3.

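### Part B SAP 5.8 deducts interruption days from total exposure only for subjects on 5 mg, and gives 5 mg exposure no formula of its own

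*SAP*

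**What the plan says.** Part B SAP 5.8 gives these rules.

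- **Per flare-up.** The rule reads "based treatment for each treated flare-up will be calculated from the date of first dose for the flare-up to the date of last dose". No interruption days are removed.
- **By dose level.** "Similarly, exposure to high flare-up treatment (the 20-mg dose), low flare-up treatment (the 10-mg dose), and non-flare-up treatment (5 mg) will be summarized". No separate formula follows, but months of 5 mg exposure are to be tabulated in categories from >0-3 to >12 months.
- **Total exposure, flare-up treatment only.** The per-flare-up exposures are added, so days between flare-ups drop out.
- **Total exposure, subjects who received 5 mg.** First to last dose of study drug, "adjusting for any days of study drug interruption".

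Both totals are described as a count of days exposed and are summarized for the Treated Population. Section 5.6 expects gaps in flare-up dosing, because it tabulates "the number of flare-ups for which an interruption of study drug occurred during flare-up dosing".

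The Part C SAP writes its deductions out. In 3.2.3 the first-to-last interval of a flare-up cycle is reduced by "days where flare-up meds were not taken/interrupted during the flare-up cycle + 1". In 3.2.4 the interval on 5 mg is reduced by "duration of flare-up treatment (days) - days where non-flare-up meds were not taken/interrupted + 1". In both, the final + 1 makes the day count inclusive.

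**The concern.** A first-to-last-dose span measures the length of a treatment episode. It equals days exposed only if no dose is interrupted. Part B uses the span for one kind of subject and the interruption-adjusted count for the other, then puts both in the same summary. The Treated Population is stratified in 4.2 into 20/10 mg only, 20/10 mg with prior non-flare-up treatment, and non-flare-up treatment only. The change of rule therefore coincides with the strata being set side by side, and a difference in exposure between strata could come partly from the definition.

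The 5 mg table raises a second question. Part B SAP 2.3 has adults resume 5 mg once a flare-up has resolved, so flare-up courses can lie between a subject's first and last 5 mg dose. Section 5.8 does not say whether those days are removed. If they are not, the error grows with the number of flare-ups.

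**Working it through.** **1. The plan's own example (Part B SAP 5.9).** Inputs: 5 mg started on Day 1, flare-up treatment started on Day 11, Part B completed on Day 174, one 84-day course.
- Actual dose: 90 × 5 + 28 × 20 + 50 × 10 = 1510 mg.
- Expected dose: 90 × 5 + 28 × 20 + 56 × 10 = 1570 mg.
- Compliance: 1510 / 1570 = 96.2%, as printed.
- Expected 5 mg days: 174 − 84 = 90, as printed. For compliance, then, the plan does remove flare-up days from 5 mg time.

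**2. Interruption days in flare-up exposure.** Take a course with a calendar span of 84 days and g interrupted days. The 5.8 span gives 84; days exposed are 84 − g. The lengths g are assumed, since the document gives none.

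| g (days) | Span | Days exposed | Overstatement |
|---|---|---|---|
| 7 | 84 | 77 | 84/77 = 1.091, 9% |
| 14 | 84 | 70 | 84/70 = 1.200, 20% |
| 21 | 84 | 63 | 84/63 = 1.333, 33% |

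Now give two subjects the same 84-day course with the same 14-day gap. In total exposure the flare-up-only subject contributes 84 days for that course. The subject on 5 mg contributes 70, reading the adjustment as a deduction. For the second subject the per-flare-up table still shows 84, so that subject's own two figures disagree.

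**3. 5 mg exposure in the 5.9 example.** Assume that the last 5 mg dose is on Day 174 and that no 5 mg dosing is interrupted. The flare-up course runs from Day 11 to Day 94 (94 − 11 + 1 = 84 days).
- Span rule applied across the study: 174 − 1 + 1 = 174 days.
- Flare-up course removed: 174 − 84 = 90 days.
- Ratio: 174 / 90 = 1.93, an overstatement of 93%.
- In months, borrowing the 30.5-day factor that 5.1 gives for participation: 174 / 30.5 = 5.70 against 90 / 30.5 = 2.95. The subject moves from the >0-3 to the >3-6 month category.
- Consistency check: under the span rule, 5 mg and flare-up exposure add to 174 + 84 = 258 days within 174 days of participation.

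Step 2 follows from stated rules. Step 3 depends on how an unstated rule is read.

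**The case against.** The strongest objection concerns 5 mg exposure. A reader might infer that 5.8 counts 20/10 mg courses as 5 mg exposure. The document does not say so. *Similarly* is attached to the summarizing and may carry over only the manner of summary. Even if the calculation carries over, it is a per-episode rule, and an episode of 5 mg treatment contains no flare-up course. The surrounding text also points the other way: 5.9 expects 5 mg only on days without flare-up treatment, and 7.1 assigns adverse events to the non-flare period only when the patient is not under flare-up treatment. This stands. What remains is that a tabulated quantity has no formula.

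A second objection is that a first-to-last-dose span is a common convention. Part A SAP 6.8 uses it too, and interruptions are visible elsewhere, in the 5.6 and 5.8 counts and in mg compliance. That would defend a span applied to everyone. It does not defend two rules for one quantity within one paragraph.

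A third is that little depends on these durations. Adverse events in 7.1 are counts and percentages of subjects, the flare-up rate in 7.1.1 uses months of follow-up, and compliance in 5.9 uses mg taken. This also stands, and it limits the reach of the point.

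**Conclusion.** The inconsistency in total exposure is in the stated rules: the same interruption counts as exposure for a flare-up-only subject and not for a subject on 5 mg. For one 84-day span, the overstatement is 9%, 20% or 33% at assumed interruptions of 7, 14 or 21 days. How often interruptions occur, and for how long, cannot be learned from the document.

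The 5 mg point holds as a missing definition. The 174 against 90 days shows what one reading would produce. It rests on that reading and on a last 5 mg dose on Day 174, and it is not evidence that the table will be built that way.

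It would also be too much to infer that adverse event incidence, flare-up rates, compliance or efficacy are distorted, since none of them uses these durations. The effect is confined to descriptive exposure summaries and to their comparability between Part B strata and with Part C. It should be corrected, because exposure is the context in which safety by regimen is read and the correction is cheap.

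**What to change.** Write the formulas into Part B SAP 5.8.

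- **Flare-up exposure (overall, 20 mg and 10 mg)** = last dose − first dose + 1 − interrupted days. Use this in the flare-up-only total, so that one interruption rule applies to both kinds of subject.
- **5 mg exposure** = last 5 mg dose − first 5 mg dose + 1 − the full calendar span of flare-up courses inside that interval − interrupted 5 mg days.
- State which missed days count as interrupted.

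The Part C formulas should not be copied verbatim. Section 3.2.4 subtracts flare-up duration that 3.2.3 has already reduced by interruptions. In an 84-day course with a 14-day gap it removes 70 days and leaves 14 in 5 mg time, unless those days are also recorded as 5 mg days not taken. It also subtracts all flare-up cycles, including any before the first 5 mg dose. Subtracting the full span of only the courses inside the 5 mg interval avoids both problems.

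The cost is SAP wording and derivation code, since 5.6 and 5.8 already rely on dose and interruption data. Reported exposure becomes shorter for subjects with interruptions.

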2.2 Study Population

A total of approximately 60 subjects will be enrolled in Part B including approximately 40 subjects who completed Study PVO-1A-201 and up to 20 new Adult Cohort subjects. The Adult Cohort will include subjects with at least 90% skeletal maturity, regardless of age; the Pediatric Cohort will include subjects with less than 90% skeletal maturity, regardless of age. Any Pediatric Cohort subject who achieves $\geq 90\%$ skeletal maturity during Part B may be considered for enrollment into the Adult Cohort at the discretion of the Investigator.

Flare based analyses will include the treatment groups: PVO 20/10 mg, Prior Non-Flare-up/PVO 20/10 mg, and Combined PVO 20/10 mg (=PVO 20/10 mg + Prior Non-Flare-up/PVO 20/10 mg groups). PVO 20/10 mg is defined as flare-ups that did not have prior non-flare-up treatment. Prior Non-Flare-up/PVO 20/10 mg is defined as flare-ups that were treated with Non-Flare-up 5 mg treatment prior to the start of the flare-up treatment. It is important to mention that the flare-up analyses is based on flare-ups, thus subjects may be included in both treatment groups, depending on when non-flare-up dosing began.

WBCT analyses are based on the PVO Non-Flare-up/PVO 20/10 mg treatment group and will include the following subsets: Treated Flare-ups, Under/Untreated Flare-ups, No Flare-ups, and Combined Treated/No Flare-ups.

Only subjects with Non-Flare-up treatment are imaged using WBCT, thus only the PVO Non-Flare-Up/PVO 20/10 mg treatment group is present. This treatment group is subset into 3 different treatment groups, depending on whether or not the subjects had treated, untreated or no flares during the duration between the baseline and Month 12 WBCT scans. Treated Flare-ups are defined as subjects who received non-flare-up/flare-up regimen for all flare-ups. Under/Untreated Flare-ups are defined as subjects who did not receive palovarotene dosing for all flare-ups. No flare-ups are defined as subjects who received the non-flare-up regimen and did not report any flare-ups.

Safety treatment groups include the PVO 20/10 mg and Non-Flare-up 5 mg groups.

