5.9.3 Total Exposure to Study Drug for Each Subject

Total exposure to study drug for each subject for Treated Population will be calculated as duration of non-flare-up treatment and flare-up treatment (see Section 3.2.3 and 3.2.4 for calculation).

Total actual dose (mg) will be summarized by Enrolled Population.

- Total dose is calculated as the cumulative dose (mg) across all dosing regimens (non-flare-up and flare-up) for each subject.
- Total non-flare-up dose is calculated as the cumulative dose across all the non-flare-up treatment periods.
- Total flare-up dose is calculated as the cumulative dose taken across all flare-up cycles.
- All total dose calculations account for weight-adjusted doses, dose reductions

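### Part B total exposure for subjects who ever took 5 mg runs from first to last dose of any study drug, so a planned off-drug gap before 5 mg began is, on the natural reading, counted as exposure

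*SAP*

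**What the plan says.** Part B SAP, section 5.8, opens its paragraph on total exposure with the target: "Total exposure to study drug for each subject will be calculated as the number of days exposed to study drug". Two rules follow.

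- Flare-up treatment only: the exposure of each flare-up is summed, with the remark "Note that this calculation excludes days between flare-ups".
- Any non-flare-up (5 mg) dosing: here "total exposure is calculated from the date of first dose of study drug to the date of last dose of study drug". The clock starts at the first dose of any study drug, not at Non-Flare-up Day 1, although section 3.7 defines that day. The sentence closes with a qualifier, "adjusting for any days of study drug interruption".

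Part B gives no definition of interruption. Where it counts interruptions it ties them to a regimen: "the number of flare-ups for which an interruption of study drug occurred during flare-up dosing" (section 5.6) and "The number of subjects who experienced an interruption of study drug during non-flare-up dosing" (section 5.8).

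Section 2.2 allows for a treated flare-up before 5 mg starts: "subjects may be included in both treatment groups, depending on when non-flare-up dosing began". It also lets a Pediatric Cohort subject who reaches 90% skeletal maturity during Part B be considered for the Adult Cohort, at the Investigator's discretion. Section 2.4 says that subjects not on non-flare-up dosing go untreated unless they have an eligible flare-up. The introduction to section 7 classes time between flare-ups without 5 mg as no treatment for adverse event grouping.

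**The concern.** The span rule gives days on drug only if the subject was on drug, or in a recorded interruption, throughout the span. That holds for an adult who starts 5 mg at the outset and returns to it after each flare-up course. It need not hold for a subject who finishes a flare-up course, spends time off drug as planned, and starts 5 mg later. For that subject the rule departs from the section's own target.

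Two inconsistencies follow. The same kind of off-drug day is excluded for flare-up-only subjects and included for mixed-regimen subjects in one Treated Population summary. And a day in the gap is no-treatment time when adverse events are grouped but an exposed day in the exposure table. At stake is the accuracy and comparability of the total-exposure summary.

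**Working it through.** **No printed figure to reproduce.** The SAP gives no worked exposure total. The compliance example in section 5.9 does supply a dosing schedule for a case where the span rule should work: 5 mg from Study Day 1, an 84-day flare-up course from Study Day 11, completion on Study Day 174. Span = 174 days. Expected dosing days = 84 + 90 = 174. The two agree, so the rule is sound for a subject on 5 mg from the start.

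**The case where it is not.** Inputs:

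- Flare-up course: 84 days (section 2.4, no extension).
- Gap *g* between the end of the course and the first 5 mg dose: not in the documents, assumed.
- Days on 5 mg, *d*: not in the documents, assumed. No interruption and no further flare-up.

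Formulas:

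- Rule as written, with the gap not treated as an interruption: last dose date − first dose date + 1 = 84 + *g* + *d*.
- Days on drug: 84 + *d*.
- Overcount: *g*, or *g* / (84 + *d*) in relative terms.

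| Days on 5 mg (assumed) | Gap (assumed) | Rule as written | Days on drug | Excess |
|---|---|---|---|---|
| 300 | 60 | 84 + 60 + 300 = 444 | 384 | 60/384 = 16% |
| 300 | 200 | 84 + 200 + 300 = 584 | 384 | 200/384 = 52% |
| 365 | 30 | 479 | 449 | 6.7% |
| 365 | 90 | 539 | 449 | 20.0% |
| 365 | 180 | 629 | 449 | 40.1% |
| 180 | 30 | 294 | 264 | 11.4% |
| 180 | 90 | 354 | 264 | 34.1% |
| 180 | 180 | 444 | 264 | 68.2% |

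Section 2.3 anticipates about 18 to 24 months of participation, so gaps of this order are possible. The documents do not say that they occurred.

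**Is Part C a usable model?** Part C SAP, section 5.9.3, says that total exposure "will be calculated as duration of non-flare-up treatment and flare-up treatment", pointing to sections 3.2.3 and 3.2.4. Section 3.2.4 takes the span from first to last 5 mg dose and subtracts the duration of flare-up treatment, which section 3.2.3 totals over all flare-up cycles. No condition limits the subtraction to cycles inside the 5 mg span. For the subject with 84 flare-up days before 300 days of 5 mg:

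- 5 mg duration = 300 − 84 = 216.
- Total = 216 + 84 = 300, against 384 on drug: 84 days too few (84/384 = 22%).

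Adding the two durations is the right principle, but the Part C formula read literally errs in the other direction.

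**The case against.** The strongest reply is that the interruption clause already deals with this. The paragraph's first sentence sets days exposed as the target, interruption is undefined, and a programmer guided by that target could remove the gap. This stands in part: the text does not force the overcount, and the result turns on how an undefined word is read. But Part B uses the word only for events during flare-up or during non-flare-up dosing, and planned time after one regimen ends and before another begins is neither. For flare-up-only subjects the authors added an explicit sentence to exclude such gaps; for mixed-regimen subjects there is none.

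A second reply is that little depends on the figure, and that stands. A reader might infer that total exposure is the base for interpreting Part B safety. The documents do not support this. Section 7.1 reports adverse events as counts and percentages of subjects by period, and section 7.1.1 divides flare-ups by subject-months of follow-up. Section 5.8 also summarizes flare-up, 20 mg, 10 mg and 5 mg exposure separately, and those summaries do not use the span rule.

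A reader might also extend the point to an off-drug stretch after 5 mg was stopped and before a later flare-up course. That is weaker, because drug stopped and later resumed fits the ordinary meaning of interruption and could be covered by the clause.

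**Conclusion.** The point holds as a minor defect in a derivation rule. For a subject with a flare-up course completed before 5 mg began, section 5.8 on its natural reading overstates total exposure by exactly the length of the gap. Under the assumptions shown, that is between 6.7% and 68.2%.

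This rests on the gap not being treated as an interruption and on at least one subject having that sequence. Section 2.2 says the sequence can happen; it would be wrong to infer that it did, or how often. The affected output is the descriptive total-exposure summary for mixed-regimen subjects and its comparability with flare-up-only subjects. Adverse event percentages, the flare-up rate and all efficacy analyses are untouched.

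**What to change.** Replace the two rules in Part B section 5.8 with one for every subject: total exposure is the number of distinct days on any study drug. Operationally, this is all flare-up treatment days plus the days from Non-Flare-up Day 1 to the last 5 mg dose, removing from that 5 mg span only the flare-up days and interruption days that fall inside it. Interruption days within a flare-up course are likewise not counted. State that days between regimens are excluded, and define interruption.

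Do not import Part C sections 3.2.4 and 5.9.3 as they stand. If they are kept for Part C, limit the subtraction there to flare-up days inside the 5 mg span.

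The cost is a sentence or two in the SAP and a small programming change. Totals fall only for subjects with an off-drug gap that would otherwise have been counted.
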